6.1 Summary of CLASSIC MS

This Phase IV, low-interventional, multicenter, ambispective study will involve the evaluation of medical records of study participants treated with Cladribine Tablets or placebo (IMP) in the previously conducted parent studies. Long-term retrospective data will be collected through evaluation of medical charts/records, and additional prospective data will be collected. No IMP will be administered as part of this study. A total of 1943 patients has been enrolled in the parent studies, 1326 from CLARITY (including 867 enrolled in CLARITY-EXT) and 617 from ORACLE MS. This study will collect data from study participants with MS who participated in the CLARITY/CLARITY-EXT clinical trial(s) and who received ≥ 1 course of IMP, or study participants with their First Clinical Demyelinating Event (FCDE) who were randomized in the ORACLE MS study and received ≥ 1 course of IMP.

Participants are invited to up to 3 clinic visits for this study. The first visit is the Screening Visit.

The following screening activities may be administered by telephone if the patient is unable and/or not willing to attend clinic for the visit, depending on approval by Ethics Committees (ECs), Institutional Review Boards (IRBs), and/or local regulations: Informed consent (for patients participating in retrospective data collection only, local requirements for patient consent will be observed, which may include informed consent form [ICF] waiver), sociodemographic and clinical characteristics, medical and disease history, and study inclusion/exclusion determination.

Figure 1: CLASSIC study Overview Diagram

6.2 Summary of Parent Studies

CLARITY (25643): The CLARITY (CLAdRibine Tablets treating MS orally) study was a multicenter, randomized, double-blind, three treatment group study of 96 weeks duration. Depending on their body weight, subjects took 1 or 2 cladribine 10 mg tablets (or matching placebo) per day over 4 to 5 days in either (a) Week 1 and Week 5 of Years 1 and 2, or (b) in Weeks 1, 5, 9, and 13 of Year 1, followed by Weeks 1 and 5 of Year 2, for a cumulative dose of 3.5 and 5.25 mg/kg, respectively. The primary objective of the trial was to evaluate the efficacy of cladribine versus placebo in the reduction of qualifying relapse rate during 96 weeks of treatment in subjects with RRMS. The secondary objectives were to assess the effect of cladribine on progression of disability (EDSS) and lesion activity as measured by MRI.

CLARITY EXT (27820): The CLARITY EXT (CLAdRibine Tablets treating MS orally EXTension) study was a randomized, double-blind, 96-week Extension study to evaluate the long-term safety and efficacy of oral cladribine in subjects with RRMS who had completed the CLARITY study. In the CLARITY EXT study, only the lower dose of cladribine was administered (subjects took 1 or 2 cladribine 10 mg tablets (or matching placebo) per day over 4 to 5 days in Week 1 and Week 5 of Years 1 and 2, for a cumulative dose of 3.5 mg/kg). Subjects who were assigned to the placebo arm in CLARITY were assigned to cladribine treatment. Subjects who received cladribine in CLARITY were randomized to either placebo or cladribine 3.5 mg/kg treatment groups in a 1:2 ratio, creating 5 arms:

Cladribine high/low dose (HLLL): Subjects who were randomized to cladribine high dose with 1 or 2 cladribine 10 mg tablets per day over 4 to 5 days in Weeks 1, 5, 9, and 13 of Year 1, followed by Weeks 1 and 5 of Year 2 of the CLARITY study (25643) (total dose 5.25 mg/kg), and to cladribine low dose with 1 or 2 cladribine 10 mg tablets per day over 4 to 5 days in Week 1 and Week 5 of Years 1 and 2 of the CLARITY extension study (total dose 3.5 mg/kg).

Cladribine low/low dose (LLLL): Subjects who were randomized to cladribine low dose with 1 or 2 cladribine 10 mg tablets per day over 4 to 5 days in Week 1 and Week 5 of Years 1 and 2 of the CLARITY study (25643) (total dose 3.5 mg/kg), then to cladribine low dose with 1 or 2 cladribine 10 mg tablets per day over 4 to 5 days in Week 1 and Week 5 of Years 1 and 2 of the CLARITY extension study (total dose 3.5 mg/kg).

Cladribine high/placebo (HLPP): Subjects who were randomized to cladribine high dose with 1 or 2 cladribine 10 mg tablets per day over 4 to 5 days in Weeks 1, 5, 9, and 13 of Year 1, followed by Weeks 1 and 5 of Year 2 of the CLARITY study (25643) (total dose 5.25 mg/kg), and then to placebo for the years 1 and 2 of the CLARITY extension.

Cladribine low/placebo (LLPP): Subjects who were randomized to cladribine low dose with 1 or 2 cladribine 10 mg tablets per day over 4 to 5 days in Week 1 and Week 5 of Years 1 and 2 of the CLARITY study (25643) (total dose 3.5 mg/kg), then on placebo for the years 1 and 2 of the CLARITY extension study.

Placebo/Cladribine low dose (PPLL): Subjects who were randomized to placebo for the first and second year of CLARITY study (25643), then to cladribine low dose with 1 or 2 cladribine 10 mg tablets per day over 4 to 5 days in Week 1 and Week 5 of Years 1 and 2 of the CLARITY extension study.

Due to administrative reasons, there was a varying period (median time 41 weeks, range 1 day to 118 weeks) between a subject completing the CLARITY study and starting in the CLARITY EXT study, subjects did not receive cladribine during this time period. Following the end of the 96-week CLARITY EXT study period, subjects were followed for safety for an additional 24 weeks. The primary objective of this trial was to evaluate the safety of extended treatment with oral cladribine when administered to subjects who completed CLARITY (25643).

ORACLE MS (28821): The ORACLE MS (ORAl CLadribine in Early MS) study was a Phase III, randomized, double-blind study to evaluate the safety and efficacy of oral cladribine tablets as a monotherapy in subjects at risk of developing MS (subjects who have experienced a first clinical event suggestive of MS). Subjects were randomized to either oral cladribine high dose with 1 or 2 cladribine 10 mg tablets per day over 4 to 5 days in Weeks 1, 5, 9, and 13 of Year 1, followed by Weeks 1 and 5 of Year 2 (total dose 5.25 mg/kg), or oral cladribine low dose with 1 or 2 cladribine 10 mg tablets per day over 4 to 5 days in Week 1 and Week 5 of Years 1 and 2 (total dose 3.5 mg/kg), or matching placebo. The design was a time-to event design with treatment schedules dependent on conversion to clinically definite multiple sclerosis (CDMS) according to the Poser criteria at any time during the first 96 weeks:

Subjects who converted to CDMS according to the Poser criteria at any time during the first 96 weeks (i.e., during the double-blind period) stopped the blinded study drug and entered an open-

label maintenance period, where they were offered open-label IFN- β and underwent evaluations for safety and efficacy.

All other subjects were planned to continue their blinded treatment up to the end of the first 96 weeks double-blind period (end of Year 2).

At the end of the first 96 weeks double-blind period, McDonald MS 2005 was assessed for all subjects and treatment schedules depended on the outcome:

- Subjects who converted to McDonald MS criteria were allocated to receive open-label oral cladribine (3.5 mg/kg) administered with 1 or 2 cladribine 10 mg tablets per day over 4 to 5 days in Week 1 and Week 5 of Years 1 and 2 (total dose 3.5 mg/kg) of the extension phase.
- Subjects who did not convert McDonald MS criteria at end of Week 96 were to be followed without treatment.
- At any time during the Extension phase, open-label cladribine with 1 or 2 cladribine 10 mg tablets per day over 4 to 5 days in Week 1 and Week 5 of Years 1 and 2 (total dose 3.5 mg/kg) if conversion to McDonald MS criteria or IFN- β (if conversion to CDMS) may have been used following the rule above.

The ORACLE MS was terminated earlier than planned in October 2011. No further dosing of blinded study medication or open-label cladribine was allowed (open-label IFN- β was offered for subjects who converted to McDonald MS). Subjects were to complete the end of trial visit assessments after a safety follow-up period of 24 weeks from the time of last dose of blinded study medication or open label cladribine.

6.3 Source Database

This analysis will use SDTM and ADAM data of each of the parent study and SDTM data of the CLASSIC study. At the time of this working document all parent studies were completed.

6.4 Interim Analyses

An interim analysis was planned to publish results when data from 50% (100 is minimum required) patients were available from cohort A (see section 8.1 for definition of Cohort). This data included the primary and selected secondary endpoints (or their components) as well as the EQ-5D-3L analysis (see Section 14 for further details on analyses and appendix 17.1 for outputs provided); pharmacogenetics and MRI were not planned to be included in the interim analysis. Results of the interim analysis have been disseminated per dissemination plan of the study, but no formal study report has been written.

6.5 Final Analysis

All analyses described in this IAP will be performed after the final database lock (see Section 14

for further details on analyses) and summarized in final study report. Results of the final analysis will be summarized in a formal study report.

7 Changes to the Planned Analyses in the Clinical Study Protocol

There are no changes to the analyses planned per protocol.

8 Analysis Populations and Subgroups

8.1 Definition of Analysis Populations

The analysis populations are specified below. Four patient cohorts will be used for the purpose of exploring all objectives of the study protocol. These will include:

- **Cohort A:** Patients who meet both the protocol inclusion and exclusion criteria and are drawn from the pooled CLARITY, CLARITY-EXT and ORACLE MS clinical trials
- **Cohort B:** Patients who meet both the protocol inclusion and exclusion criteria and are drawn from the CLARITY or CLARITY-EXT study only
- **Cohort C:** Patients who meet both the protocol inclusion and exclusion criteria and are drawn from the CLARITY-EXT (and Clarity) study only
- **Cohort D:** Patients who meet both the protocol inclusion and exclusion criteria and are drawn from the ORACLE MS study only

The parent study identification is specified in the demographic eCRF page and will be used to identify cohort. If the parent study identification is missing, then the participant will not be included in any cohorts/analysis.

Patients will be analyzed according to their actual exposure/no exposure to oral Cladribine in the parent study. For Oracle patients, treatment during initial treatment period and open label are used for this categorization.

8.1.1 Full Analysis Set

The full analysis set (FAS) will include all patients participating in CLASSIC study (randomized in CLARITY and have received ≥ 1 course of IMP [Cladribine Tablets or placebo] or patients randomized in the ORACLE study and have received ≥ 1 course of IMP).

Patient who have received ≥ 1 course of IMP will be identified using a list of patients provided to sites by the sponsor. Patients enrolled in the study but did not complete 1 course of IMP will be considered protocol deviation.

There will be no per-protocol analysis population excluding patients with protocol deviations.

8.1.2 The MRI Sub-Study Analysis Set (MRISS)

The MRI Sub-Study Analysis population includes all FAS participants who signed the MRI sub-study informed consent (Optional Informed Consents eCRF page).

The MRISS population will be used on second and tertiary endpoints related to MRI analysis. Please see section 14 for further details.

8.1.3 The Whole Parent Study population (WPS)

The WPS population include all parent study patients (enrolled in CLASSIC or not) randomized in CLARITY or ORACLE who have received ≥ 1 course of IMP (Cladribine Tablets or placebo) *. The WPS population will be used to evaluate potential selection bias described in Section 9 of the protocol. This population will exclude CLASSIC patients who did not receive ≥ 1 course of IMP (important protocol deviations).

*One course of IMP is defined as 2 treatment weeks. A treatment week is defined as daily administration of IMP given consecutively over 4-5 days during a 28-day period.

8.1.4 The pharmacogenetic population (PGX)

The PGX population includes all FAS participants who signed the informed Consent for optional pharmacogenetic testing (Optional Informed Consents eCRF page) and provided suitable blood sample.

8.2 Subgroup Definition and Parameterization

8.2.1 Parent Study Treatment groups

Analyses will be performed on the "as treated principle", where patients are allocated to the treatment that they actually received in the parent study (which may be different from the study treatment to which they were randomized to).

- **Parent study never exposed to cladribine:** if a subject has taken only placebo in all studies, then her/his data becomes part of the "Never exposed to cladribine" parent study treatment group. A subject who switches treatment from placebo to cladribine in subsequent studies/periods **will not** be considered in this group.
- **Parent study exposed to cladribine:** patients with at least one dose of cladribine. Subjects who were on placebo during the clinical trial and switched to cladribine in the extension study will contribute to the parent study treatment group "Exposed to cladribine".

For Oracle patients, treatment during initial treatment period and open label are used for this categorization.

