To define (b), (c) and (d): If at least 1 dose of Cladribine has been administered after end of Year 1, for CLARITY or CLARITY EXT then the participant will be considered starting the second treatment course (year). If at least 1 dose of Cladribine has been administered during the first year of CLARITY EXT after receiving at least 1 dose during the second treatment course of CLARITY, then the participant will be considered starting the third treatment course (year). Individual parent study datasets will be used.

2. Long-term Responder/Non-responder:

a. Primary definition

- **Long-term Responder:** Study participants not requiring DMD 4 years or later following their last dose of IMP, and who did not demonstrate any evidence of disease reactivation based on Investigator assessment of clinical and imaging outcomes
- **Non-Responder:** Study participants requiring DMD less than 4 years following their last dose of IMP or who demonstrate any evidence of disease reactivation based on Investigator assessment of clinical and imaging outcomes.

Computation rules:

Prior/concomitant medication eCRF page and “physician sequential treatment decision questions” eCRF page question 8 and 9 to be used to identify the date of the DMD received.

4 years after last dose of IMP = Last dose of IMP date + 4*365.25 days

Evidence of disease reactivation will be defined by either:

- a) MRI lesions: new T1 lesion or new T2 lesion reported
- b) New Relapse reported
- c) EDSS worsening defined as an EDSS score increase of at least 1 point between 2 consecutive visits of at most 365 days (if 2 consecutive EDSS assessments are separated by more than 365 days then EDSS cannot be used in the criteria and will be considered as missing/not reported).

New relapse, MRI lesions and EDSS worsening will be identified utilizing dates in parent studies for the period between last dose of IMP and end of parent study.

For the period following the end of the parent study until SV1 of Classic study the following source data will be used:

- 1) MRI lesion by the eCRF “frequency stable patient monitoring questions” (fspmq) page,

Q4/Q3. If Q4 is answered “yes” the date will be taken from Q3 and determined if the MRI lesion is before the 4 years since last IMP.

- 2) New relapse will be identified using the eCRF “MS Relapse history” page(hxrelap) Q2.2.
- 3) The EDSS worsening by the eCRF “expanded disability status scale (edssr) for retro data” page.

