9.3 Timepoints

- **Date of First dose of IMP (FDIMP)** is the day of start of first study drug intervention (placebo or cladribine).
- **Date of Last dose of IMP (LDIMP)** is the day of end of study drug intervention (placebo or cladribine). For ORACLE patient both ITP and open label period will be observed to identify the end of study drug intervention.
- **The end of the parent study** is defined as the last date of data collection from the parent study.

- **Baseline** (of parent study) is defined as PSD1 baseline, which is the last assessment prior to or at FDIMP.

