11.2 Medical History

The medical history will be summarized from the “Medical History details” eCRF page, using MedDRA, preferred term as event category and system organ class (SOC) body term as Body System category. Each participant will be counted only once within each PT or SOC.

Listing will also be provided.

12 Previous or Concomitant Medications/Procedures

Previous or concomitant medication will be presented based on FAS analysis set for Cohort A and will be presented by ATC and Preferred Name, per parent study exposed group and total. Listing will also be provided.

Previous and concomitant medications are medications, other than parent study medications (i.e. cladribine or placebo), which are taken by patients any time on-trial before or on or after CLASSIC Study Visit 1.

Handling of missing or partial dates are critical for medications identified as DMD that will determine timing of DMD in responders/non-responders and prior DMD use variables. All missing/incomplete dates will be imputed as described in Section 9.5.

Medications in CLASSIC

Medications in CLASSIC are medications which are taken by subjects at any time after (>) the end of the parent study day. Reporting will be done for Cohort A, FAS analysis set.

Disease modifying drugs in CLASSIC

MS-DMDs drugs will be identified using lookup list against all concomitant medication reported as well as eCRF dedicated question. Coding group will provide initial list using drug code, ATC and other elements for the medical team to review and approve prior to data base lock. Final list will be similar to table 3 below and will be standalone document (Appendix 17.2). First, Second, third and any subsequent DMD after first and last dose of Cladribine will also be reported descriptively. Each one will be identified based on the date of the DMD in ascending order since the date of first dose of IMP. First subsequent DMD will be reported by DMD type and ATC and second and third subsequent DMDs will be reported by DMD type only. First subsequent DMD will also be summarized by type, ATC and Medication Name. Patterns of DMD switches will be described also and provided only for the final analysis. Reporting will be done for all cohort, FAS analysis set.

A listing of subsequent DMDs after last IMP dose will be provided for subjects with repeating DMD types.

Table 4: List of MS-DMD

Drug Name	ATCs	SDGs (Standard Drug Groupings)

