14.3.2 Durability of clinical outcomes

Durability of clinical outcomes will be summarized descriptively and evaluated via retrospective data collection from medical records or at Study Visit 1:

- Proportion of study participants being bedridden
- Time from first dose of IMP to first use of an ambulatory device
- Time from last dose of IMP to first use of an ambulatory device
- Time from first dose of IMP to first use of a wheelchair
- Time from last dose of IMP to first use of a wheelchair
- Number of MS relapses between the end of parent study to Study Visit 1
- ARR from time of first dose of IMP to SV1, and by 2-year intervals
- ARR from time of last dose of IMP to SV1, and by 2-year intervals
- % and Time to conversion to CDMS (For Cohort D participants only)
- Proportion of study participants diagnosed as Secondary Progressive MS (SPMS) without relapses in the 3 months prior to SPMS diagnosis
- Proportion of study participants diagnosed as SPMS with relapses in the 3 months prior to SPMS diagnosis
- Proportion of study participants diagnosed as Primary Progressive MS (PPMS) (For Cohort D participants only)

Computational rule:

Participants being bedridden, first use of an ambulatory device and first use of a wheelchair are collected on “ambulatory - bedridden status and first use of wheelchair” eCRF page.

Participants diagnosed as SPMS with and without relapses in the 3 months prior to SPMS diagnosis are collected on “History of MS onset” eCRF page and Participants diagnosed as PPMS are collected on “conversion to CDMS” eCRF page.

Time to first ambulatory device/wheelchair

Kaplan Meier curve and estimates including number of subjects at risk, number of subjects with an event and subject censored will be presented for time to first ambulatory and wheelchair from first and last dose of IMP administered, by treatment group (exposed vs never exposed) and overall

Computation rule:

Whichever come first will be considered as an event:

- 1) CRF Ambulatory device page, wheelchair use date
- 2) CRF Ambulatory device page, ambulatory device use date
- 3) EDSS score ≥ 6
- 4) Death due to MS

Kaplan Meier SAS code:

AVAL = time-to-event response variable

CENSOR = censoring variable (0 = event, 1 = no event)

TRT= Trt group (“Exposed to Clad” “Never exposed to Clad”)

Code:

```
PROC LIFETEST DATA=ADTTE OUTSURV=RESULTS ALPHA=0.05 METHOD= KM Conftype =  
Loglog;  
TIME AVAL*CENSOR(1);  
STRATA TRT;  
RUN;
```

Annualized Relapse Rate:

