ARR from time of FDIMP to Study Visit 1 is calculated for each treatment group:

$$\text{ARR} = [(\text{sum of relapses} * 365.25) / (\text{sum of time on study in days until SV1})]$$

ARR from time of FDIMP to Study Visit 1 and by 2-year intervals is calculated for each treatment group:

$ARR = [(sum\ of\ relapses\ *365.25) / (sum\ of\ time\ on\ main\ study\ by\ 2\text{-}year\ intervals\ in\ days\ until\ SV1)]$

Time on study = Study Visit 1 – first dose of IMP +1

ARR from time of last dose of IMP to Study Visit 1 will be calculated similarly.

Table 5: Time window for ARR by 2-year intervals

Cumulative intervals	Time intervals
Less than 2 years	1 to 730 days
2 nd years to 4 th years	731 to 1461 days
4 th years to 6 th years	1462 to 2191 days
6 th years to 8 th years	2192 to 2922 days
X th years to Y th years...	Truncate (X*365.25 +1) to truncate (Y*365.25) days

Time to CDMS (Cohort D only)

Number of participants who converted to CDMS since first and last dose administered will be summarized descriptively.

Both information collected in “Conversion to CDMS” eCRF page and ORACLE MS parent study dataset will be used to identify participants who converted to CDMS after first/last dose of IMP.

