Table 15.2.4.4.1	MRI characteristics at Study Visit 2 of long-term responders vs non-responders – Cohort D- MRISS analysis set		
Table 15.2.4.4.2	MRI characteristics at Study Visit 2 of long-term responders vs non-responders – Cohort D – MRISS analysis set (Sensitivity Def B)		
Table 15.2.4.4.3	MRI characteristics at Study Visit 2 of long-term responders vs non-responders – Cohort D – MRISS analysis set (Sensitivity Def C)		

15.2.5: Tertiary Endpoint 1			
Table 15.2.5.1	Real-world treatment patterns in study participants – Cohort A- FAS analysis set		U
15.2.6: Tertiary Endpoint 2			
Table 15.2.6.1	Durability of clinical outcome– Cohort A – FAS analysis set		U
Table 15.2.6.2	Kaplan Meier- Time to first ambulatory device/wheelchair - Cohort A -FAS analysis set	Y	U
Figure 15.2.6.1	Kaplan Meier- Time to first ambulatory device/wheelchair by Exposed/Never Exposed Group - Cohort A -FAS analysis set	Y	U
Figure 15.2.6.2	Kaplan Meier - Time to First Ambulatory Device/Wheelchair - Cohort A - FAS Analysis Set	Y	
15.2.7: Tertiary Endpoint 3			
Table 15.2.7.1	Change in Quality of life outcomes – Cohort A- FAS analysis set	Y	U
Table 15.2.7.2	Change in Cognition outcomes (BVMT-R score)– Cohort D- FAS analysis set		U
Table 15.2.7.3	Change in Cognition outcomes (SDMT score) – Cohort D- FAS analysis set		U
15.2.8: Tertiary Endpoint 4			
Table 15.2.8.1	Change in MRI assessment from Baseline to Study Visit 2– Cohort A -MIRISS analysis set		U
15.2.9: Tertiary Endpoint 5			
Table 15.2.9.1	Responder rate by HDA/Non-HDA patients – Cohort B-FAS analysis set		U
15.2.10: Additional analysis			
Table 15.2.10.1	Additional analysis: Comparison between baseline characteristics from Non-CLASSIC/CLASSIC patients- WPS analysis set		U
15.2.11: PGX Analysis (tables will be repeated for each SNP or combination of SNPs.)			
Table 15.2.11.1.1	Proportion of patients using a wheelchair (EDSS>=7) the majority of the time in the 3 months prior to Study Visit 1 or bedridden – Cohort A – Subgroup with Presence of SNP1 gene - PGX Population		
Table 15.2.11.2.1	Proportion of patients with EDSS of 6.0 or higher since last dose of IMP – Cohort A – Subgroup with Presence of SNP1 gene - PGX Population		

Table 15.2.11.3.1	Clinical characteristics at Study Visit 1 of long-term responders vs Non-Responders – Cohort A– Subgroup with Presence of SNP1 gene - PGX Population		

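### Exposed includes placebo-to-cladribine switchers while the clock starts at a placebo dose, so relapse rates and Kaplan-Meier curves from first IMP dose credit pre-cladribine time to Exposed

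*SAP*

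**What the plan says.** **Grouping.** SAP 8.2.1 analyses patients as treated. One dose of cladribine is enough to be Exposed: "Subjects who were on placebo during the clinical trial and switched to cladribine in the extension study will contribute to the parent study" treatment group of that name. ORACLE MS open-label cladribine counts too. SAP 6.2 says that every CLARITY placebo patient who entered CLARITY-EXT was assigned cladribine (arm PPLL).

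**Clock.** SAP 9.3 says that first dose of IMP (FDIMP) "is the day of start of first study drug intervention (placebo or cladribine"), and that last dose of IMP (LDIMP) "is the day of end of study drug intervention (placebo or cladribine").

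**Use of the two together.** In SAP 14.3.2, "ARR from time of FDIMP to Study Visit 1 is calculated for each treatment group", overall and by two-year interval. Kaplan-Meier estimates of time to ambulatory device or wheelchair run "from first and last dose of IMP administered, by treatment group (exposed vs never exposed) and overall". SAP 17.1 lists the figure as "Time to first ambulatory device/wheelchair by Exposed/Never Exposed Group - Cohort A -FAS analysis set".

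**Responders.** SAP 8.2.2 ends the responder window at LDIMP plus four years. In parent-study data, reactivation is "identified utilizing dates in parent studies for the period between last dose of IMP and end of parent study". Arms HLPP and LLPP took cladribine in CLARITY and placebo in both CLARITY-EXT years, so their LDIMP is a placebo dose.

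**Caveat.** SAP 8.2.2 and protocol 9.3 warn against reading treatment effects from the treatment-course and subsequent-DMD subgroups. Neither names exposed versus never exposed, which the SAS code in SAP 14.1 estimates as a contrast.

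**The concern.** The group label depends on what a patient eventually received, but follow-up starts before some of those patients had received it. In the FDIMP-based outputs, relapses and first device use on placebo, or in the gap between the two CLARITY trials, are attributed to Exposed. No rule divides the time at first cladribine dose. The first two-year ARR interval suffers most, and ARR by two-year interval is a named tertiary endpoint.

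The responder definition meets the same clock from the other end. For HLPP and LLPP, reactivation between the last cladribine dose and the last placebo dose is not counted, and Year 4 lies well beyond four years from cladribine. The responder split supports two secondary endpoints (SAP 14.2.2 and 14.2.3). Sensitivity definitions B, C and D change the criteria but keep the IMP origin, so none of them tests this.

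**Working it through.** The plan gives no figure for the time or rate at issue. Two of its related figures check out. The Table 5 limits follow from truncating 2 × 365.25 to 730 and from 4 × 365.25 = 1461. The CLARITY rates of 0.33 and 0.14 (protocol 2.2) give 1 − 0.14/0.33 = 57.6%, against 57.4% stated, which is consistent with rounding.

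**1. Pre-cladribine time per CLARITY switcher.** Inputs from SAP 6.2: CLARITY lasted 96 weeks; the gap before CLARITY-EXT had a median of 41 weeks and a range of 1 day to 118 weeks. Time = 96 weeks + gap.

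| Gap | Days before cladribine | Years | Share of days 1–730 |
|---|---|---|---|
| 1 day | 96 × 7 + 1 = 673 | 1.84 | 673/730 = 92% |
| 41 weeks | 137 × 7 = 959 | 2.63 | 100% |
| 118 weeks | 214 × 7 = 1498 | 4.10 | 100% |

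At the median gap, (959 − 730)/731 = 31% of days 731–1461 is also pre-cladribine. This holds for switchers who completed the 96 weeks.

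**2. First-window Exposed ARR, Cohort A (illustration).** From SAP 6.1: 1326 CLARITY patients, 867 of them in CLARITY-EXT, and 617 ORACLE MS patients. Assumptions: 1:1:1 allocation, equal rollover in all CLARITY arms, two-thirds of ORACLE MS exposed from the start, and a rate of 0.14 on or after cladribine for everyone.

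- CLARITY switchers: 442 × 867/1326 = 289.
- Exposed: 884 + 289 + 411 = 1584, so switchers are 289/1584 = 18%.
- ARR = (289 × r + 1295 × 0.14)/(1584 + n), where r is the switchers' pre-cladribine rate and n is the number of ORACLE MS placebo patients who later took open-label cladribine.

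The n patients are taken as relapse-free before cladribine, because those who converted to CDMS in the blinded period were offered interferon beta instead. The values 25 and 100 (of about 206 placebo patients) and r = 0.25 are assumed.

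| r | n = 0 | n = 25 | n = 100 |
|---|---|---|---|
| 0.33 | 0.175 | 0.172 | 0.164 |
| 0.25 | 0.160 | 0.158 | 0.151 |

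Under the same assumptions, splitting at first cladribine dose returns 0.14.

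**3. Whole-period ARR over 10 years, r = 0.33.** With n = 0: [289 × (0.33 × 2.63 + 0.14 × 7.37) + 1295 × 1.4]/15,840 = 0.149. With n = 100 and 1.84 relapse-free years before cladribine for each, it is 0.147. The shift is about 0.01.

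**4. Responder window, HLPP and LLPP.** Last cladribine is taken at Year 2 Week 5 of CLARITY and last placebo at Year 2 Week 5 of CLARITY-EXT. The offsets cancel, so the lag is again 96 weeks + gap: 2.63 years (1.84–4.10). Year 4 then falls 6.6 years (5.8–8.1) after last cladribine. This applies to patients who completed CLARITY-EXT dosing; the lag is shorter for those who stopped early. About (867 − 289)/3 = 193 parent-study patients, 10% of 1943, were in these arms. The number in CLASSIC-MS is not known.

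**The case against.** The best defence is that the origin is the protocol's. Its endpoints define IMP as cladribine or placebo and anchor ARR and time to device at first dose of IMP, and response at last dose of IMP. The SAP follows this and applies one rule to everyone. That stands: a reader might infer that the SAP departs from the protocol, or that the responder rule is inconsistent between patients, and neither is so. The defence does not cover reporting the result by eventual exposure with no cladribine-based counterpart.

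The LDIMP versions of ARR and Kaplan-Meier do remove the pre-cladribine time for CLARITY switchers. They leave the FDIMP outputs unchanged and start HLPP and LLPP at a placebo dose.

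The study is exploratory, without formal inference, and in Cohort B the treatment-course subgroups already covered by the caveat contain the never-exposed split. This makes the missing sentence a smaller matter, but the contrast coded in SAP 14.1 is for Cohort A and is not named.

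A reader might infer immortal-time bias in favour of cladribine. The documents do not support a direction. Switchers had to complete CLARITY, yet their relapses, device use or EDSS of 6 or more on placebo count against Exposed. The CLARITY never-exposed group consists by design of patients who did not enter CLARITY-EXT, or entered and took no cladribine.

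A reader might also infer that SAP 14.1 demands an exposed/not-exposed model estimate in Cohort C, where no placebo/placebo arm existed. The section lists only disease duration as a factor for Cohorts B, C and D, so that reading is not established.

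Two related points are wording only. SAP 12 says "First, Second, third and any subsequent DMD after first and last dose of Cladribine will also be reported descriptively" but orders these drugs from first IMP dose, and the titles in SAP 17.1 already name the IMP dose. The category for placebo in both CLARITY trials may simply be empty.

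**Conclusion.** The point holds for the FDIMP-based ARR and Kaplan-Meier outputs by exposure group. Each CLARITY switcher who completed 96 weeks brings 1.84–4.10 years of pre-cladribine time into Exposed, nearly all or all of the first ARR window. The timeline follows from the documents. The first-window ARR of about 0.15–0.175 rests on the assumptions above, including 0.14 applied to ORACLE MS patients and to the higher dose, although protocol 2.2 ties it to 3.5 mg/kg in CLARITY.

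Only distortion of the Exposed rate is shown. The net direction of the exposed-versus-never contrast, of the Kaplan-Meier comparison and of any HLPP/LLPP shift in responder status is unknown. The primary proportion is little affected by the choice of clock; for it, the gap is the missing caveat. This is a low-cost improvement to descriptive outputs and does not invalidate the plan.

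**What to change.** Keep all IMP-based analyses.

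1. In SAP 14.3.2, split Exposed relapses and person-time at first cladribine dose and report the pre-cladribine part separately. Add a supplementary Kaplan-Meier from first cladribine dose in patients event-free at that date, and report how many are excluded.
2. Extend the SAP 8.2.2 caveat to exposed versus never exposed and repeat it beside the SAP 14.1 estimate.
3. Optionally, add a responder sensitivity analysis among Exposed patients only, with last cladribine dose as origin. State its two downsides: never-exposed patients have no comparable origin, and more of the HLPP/LLPP window would fall in parent-trial data, so their reactivation would be better ascertained than in PPLL, LLLL or HLLL.
4. As minor clarifications, state in SAP 12 which dose the DMD order runs from, and reconcile the category for placebo in both CLARITY trials with the five CLARITY-EXT arms.

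The cost is SAP text and programming on parent-study data already in use. First cladribine date is already needed for the Cohort B treatment courses and would be extended to ORACLE MS; last cladribine date needs a definition only for item 3. Under item 1, switchers get a later origin than never-exposed patients and the event-free restriction drops some of them, so these outputs should remain supplementary.
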